4.1 Description of Study Design

The proposed study will evaluate the effectiveness of Accessible Care (AC) for engaging and retaining PWID in care for hepatitis C, as compared with Usual Care (UC). A sample of 300 PWID with chronic hepatitis C will be recruited from the Lower East Side Harm Reduction Center, our community-based partner, and offered enrollment in a longitudinal study in which they will be randomized 1:1 to receive AC or UC. Participants will be given an appointment with a Hepatitis C Care Coordinator (AC) or referrals to existing community resources (UC), according to their study arm. To assure that any observed effects can be attributed to the intervention and not to differences in insurance, transportation, or physician characteristics, study participants in both arms will receive assistance signing up for health insurance (Medicaid); transit fare (MetroCards) as needed for appointments; and access to the same study physicians at the Weill Cornell Medical Center (WCMC) Center for the Study of Hepatitis C.

All patients who choose to receive antiviral treatment and have no contraindications will undergo state-of-the-art antiviral therapy according to standard clinical protocols. Study physicians are committed to caring for people who use drugs without shaming, blaming, or stigmatizing them or withholding care on the basis of arbitrary requirements for abstinence from substance use.

Participants in both arms will be interviewed at baseline and 3, 6, and 9 months after randomization. To assure retention in follow-up and reduce differential attrition, all patients will be seen monthly for a check-in to update contact information, as we have done in previous research. Outreach workers will help retain participants in the study by reminding them of upcoming appointments and searching for those lost to follow-up. Participants in both arms will be asked monthly if they've started antiviral therapy and those receiving antiviral therapy will be interviewed monthly while on therapy to assess adherence and side effects. Patients will receive cash stipend for each study interview or monthly check-in.

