Aim 1c. Cost of intervention: The HCCC and the Clinician will log time spent providing services, excluding research activities. Costs will be assigned to staff time based on prevailing national wage rates. Patient time costs will also be estimated based on time spent with staff members and will be valued based on the minimum wage because most patients are likely to be unemployed. We will describe patient-reported health care visits, employment, and incarceration that will be used as inputs to future cost or cost-effectiveness studies.

Aim 1d. Safety: Because concern about side effects has been cited as a reason not to treat PWID for hepatitis C, and because experience with these drugs in PWID has not been reported, we will report prospectively collected data on safety outcomes on all participants who receive antiviral therapy. All treatment-emergent side effects (e.g., fatigue, headache, nausea, insomnia, irritability, anorexia, diarrhea, constipation, etc.) will be tabulated, as will adverse events, including abnormalities in serum bilirubin, liver enzymes, infections, hospitalizations, and deaths), and any adverse effects requiring treatment discontinuation, according to OHRP152 and NIH153 guidelines. We will describe the frequency of side effects, adverse events, and treatment-limiting outcomes, among all study participants who received at least one dose of antiviral medication. If numbers permit, we will compare the rates in the two arms to see whether AC influences perceived side effects.

Aim 1e. Reinfection: We will report reinfection rates in all patients in both arms who achieve SVR using time-to-event methods. If 150 participants initiate antiviral therapy (50% overall) and 120 (80%) of those achieve SVR, with 2%/month attrition (21.5%/yr), we will have 198.3 person-years of follow-up when data collection is concluded, enough for a reasonably robust estimate.

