5. At the medical evaluation, about 20mL (4teaspoons) of blood will also be drawn by one of the other research staff members, and sent to New York Presbyterian Hospital. The blood will be tested to assess participants' health and liver. A small percentage of the blood drawn will be stored at the Weill Cornell Medical College Clinical and Translational Science Center for future testing of characteristics of your hepatitis C virus.
6. We will schedule participants to come back in 2 weeks to find out the results of your blood tests. Participants and their hepatitis C doctor will work together to make an informed decision about whether participants will take medication used to treat hepatitis C. The doctor will explain the risks and benefits of taking any medicines before you take them. The medications the doctor will prescribe are the current best standard of HCV treatment available. If the doctor recommends that the participant take these medications, participants will be free to decide whether or not to take them.
7. If participants take the medication for hepatitis C, they will get appointments to come back to pick up their medication. Hepatitis C medications prescriptions will be sent to specialty pharmacies, and when obtained, delivery of medication will be to the harm reduction facility or patients residence if novel coronavirus is an issue.
8. If participants begin treatment for hepatitis C, standard blood tests for monitoring the treatment will be performed by a members of the research staff (or commercial lab testing centres if novel coronavirus is an issue), at weeks 2, 4 and 12 of treatment, and 4 and 12 weeks after the end of treatment. In addition, an extra two teaspoons of blood may be drawn at each of these visits for research purposes and sent for storage at Cornell's Clinical and Translational Science Center. These samples may be tested to look for signs of multiple concurrent hepatitis C infections, and help to decipher treatment failure from re-infection in participants who do not achieve cure of their hepatitis C.
9. If participants start the medications used to treat hepatitis C and want to stop them before their treatment is finished, they are free to do so and will not be penalized in any way, although this could limit the success of hepatitis C treatment. Participants will be encouraged to continue with the study questionnaires every three months.

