10. Within 6 months of enrolling in the study, participants will have a one-on-one meeting with a hepatitis C study coordinator to review harm reduction practices. This discussion will include discussions on prevention of hepatitis C transmission and re-infection, ways to engage in safe injection practices and avoid cross-contamination of injection equipment while injecting with others.
11. Data from participants' clinical medical records will be entered into our research database during the course of your treatment by a members of the research staff. These data include, but are not limited to, hepatitis C genotype, hepatitis C viral load, fibrosure results(looking for signs of cirrhosis), HIV antibody, sustained virologic response (defined as no detectable hepatitis C virus 12 weeks after completing therapy), and any side effects or adverse effects you experience during therapy

If participants agree to take part in this study and are assigned to Group B, participants will have the following tests and procedures:

Group B –Usual Care Group (Hepatitis Care at usual locations in the community): If assigned to this group, participants will participate in research visits but not receive hepatitis care or treatment at the Lower East Side Harm Reduction Center as part of the study. Participants can obtain care and treatment for hepatitis C at the usual locations in the community.

Research Visits (every 3 mos): Information that will be collected for the study will consist of (1) detailed questionnaires, and (2) one or more extra blood tests. The details of the study are as follows:

1. Questionnaires will be administered every three months for up to 12 months, independent of whether participants receive treatment for your hepatitis C, with questions about their demographics (e.g., age, gender, race), their alcohol and drug use history and practices, sexual practices and experience with health care.
2. One teaspoon of your blood will be drawn and sent to New York Presbyterian Hospital –Weill Cornell Translation Science Center where it will be processed and stored for potential future testing of characteristics of your Hepatitis C virus.
3. Human Immunodeficiency Virus (HIV) testing as described above will be offered at a research visit every 6 months to those participants who previously tested negative for HIV.

Hepatitis Care and Treatment:

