4. Participants will be referred to a hepatitis C case manager (funded through the New York City Department of Health Check Hep C Program), on site at their harm reduction facility (Lower East Side Harm Reduction Center), who will assist participants with referral for hepatitis C care within the community.
5. If participants start treatment for hepatitis C during their time in the study, we will ask participants to give us permission to talk with their hepatitis C doctor so we can have access to their medical records and monitor how they are responding to treatment.
6. If participants achieve a sustained virologic response after completing hepatitis C treatment, which means that the treatment was successful, participants will be given an appointment to come back every three months to complete a study interview and be tested for hepatitis C, for up to 144 weeks after treatment completion, to find out whether they are still negative, or to see whether they get re-infected.

QUALITATIVE INTERVIEWS During the study, we may ask participants to take part in an interview about their experiences related to hepatitis C treatment. This will last about 60-90-minutes. If participants choose to participate, the interview will be digitally audio-recorded. If participants are selected for this interview we will ask participants about: health care and hepatitis C-related healthcare experiences, alcohol and drug use, injection risk behaviors and sexual practices. We will ask participants how these changed, if they did, during their taking part in the study.

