8.3 Time Period and Frequency for Event Assessment and Follow-Up

The occurrence of an AE or SAE may come to the attention of study personnel during study visits and interviews of a study participant presenting for medical care, or upon review by a study monitor. All AEs including local and systemic reactions not meeting the criteria for SAEs will be captured on the appropriate RF. Information to be collected includes event description, time of onset, clinician's assessment of severity, relationship to study product (assessed only by those with the training and authority to make a diagnosis), and time of resolution/stabilization of the event. All AEs occurring while on study must be documented appropriately regardless of relationship. All AEs will be followed to adequate resolution.

Any medical condition that is present at the time that the participant is screened will be considered as baseline and not reported as an AE. However, if the study participant's condition deteriorates at any time during the study, it will be recorded as an AE. UPs will be recorded in the data collection system throughout the study.

Changes in the severity of an AE will be documented to allow an assessment of the duration of the event at each level of severity to be performed. AEs characterized as intermittent require documentation of onset and duration of each episode.

The PI will record all reportable events with start dates occurring any time after informed consent is obtained until 7 (for non-serious AEs) or 30 days (for SAEs) after the last day of study participation. At each study visit, the investigator will inquire about the occurrence of AE/SAEs since the last visit. Events will be followed for outcome information until resolution or stabilization.

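### Aim 1d's planned arm comparison of side-effect and adverse-event rates is not limited to sources common to both arms, so chart-recorded events could inflate the Accessible Care rate

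*Combined protocol and SAP*

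**What the plan says.** Section 4.2.1, Aim 1d, tabulates side effects and adverse events and describes the frequency of side effects, adverse events and treatment-limiting outcomes "among all study participants who received at least one dose of antiviral medication". It then adds: "If numbers permit, we will compare the rates in the two arms to see whether AC influences perceived side effects". No source, test or missing-record rule is given for this comparison. Section 9.2 restates other Aim 1 outcomes but not safety, so it does not settle the matter.

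Sources in both arms:
- Section 4.1: "those receiving antiviral therapy will be interviewed monthly while on therapy to assess adherence and side effects".
- Section 8.3: "At each study visit, the investigator will inquire about the occurrence of AE/SAEs since the last visit". No arm is excepted.
- Section 4.1 also takes adverse events from the Weill Cornell electronic record or from records requested of other facilities, and gives both arms access to the same Weill Cornell physicians.

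Sources that differ by arm:
- Accessible Care (section 7.1, Group A, item 11): research staff enter data from clinical records, including "any side effects or adverse effects you experience during therapy".
- Usual Care (section 7.1, Group B, item 5): care is at community locations, and for those who start treatment "we will ask participants to give us permission to talk with their hepatitis C doctor so we can have access to their medical records". No matching list of side-effect items is stated.
- Section 8.3 says events may also "come to the attention of study personnel during study visits and interviews of a study participant presenting for medical care". In Accessible Care, presenting for hepatitis C care means presenting to the study's own on-site clinician.

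**The concern.** A difference in reported side effects between arms can arise from a difference in experience or from a difference in how many ways the study hears of an event. Accessible Care has a routine second route. Usual Care has that route only when permission is given, the records arrive and the symptom was written down. If the comparison counts every event from any route, part of the observed difference measures the number of routes.

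Aim 1d itself names concern about side effects as a cited reason for not treating people who inject drugs. An apparent excess in the on-site arm, produced by better recording, could be read as a drawback of the model being tested.

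**Working it through.** **What is being compared.** In Aim 1d, the rates in the comparison sentence refer back to the sentence before it, which covers side effects, adverse events and treatment-limiting outcomes. Section 4.1 names medical records as a source of adverse events, and Group A item 11 puts clinic-recorded side effects into the research database. Chart data are therefore a stated source for adverse events and an available source for side effects, and nothing excludes them from the comparison.

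**The plan's own figure.** None exists for safety. The power example in section 9.4 (66% versus 50% initiating, 150 per arm, 80%) reproduces at 80.5% with a two-sided 5% test. It concerns treatment initiation and is not in question here.

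**Illustration.** All capture values are assumptions. Let t be the true rate, equal in both arms; c the capture by the shared interview; and e the share of the remaining events picked up through charts.

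Observed rate = t × [c + (1 − c) × e]

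With t = 0.40, c = 0.70, e = 0.50 in Accessible Care and e = 0 to 0.25 in Usual Care:
- Accessible Care: 0.40 × (0.70 + 0.30 × 0.50) = 0.340
- Usual Care, no chart yield: 0.40 × 0.70 = 0.280
- Usual Care, half the chart yield: 0.40 × (0.70 + 0.30 × 0.25) = 0.310
- Spurious difference: 3 to 6 points
- Shortfall in Usual Care relative to Accessible Care: 0.03/0.34 = 9% to 0.06/0.34 = 18%

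**Range.** The difference is t × (1 − c) × (e in Accessible Care − e in Usual Care). Take c from 0.60 to 0.80, e in Accessible Care from 0.30 to 0.70, and e in Usual Care from zero to half of that:
- Smallest: 0.40 × 0.20 × (0.30 − 0.15) = 0.012
- Largest: 0.40 × 0.40 × (0.70 − 0) = 0.112

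The spurious difference is therefore about 1 to 11 points.

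**Chance of a nominally significant result.** The section 9.4 example implies 0.66 × 150 = 99 and 0.50 × 150 = 75 treated. Take a true rate of 40% in both arms, overall capture of 90% in Accessible Care, and a two-sided two-proportion z-test at 5%:

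| Usual Care capture | Observed rates | Chance of p < 0.05 |
|---|---|---|
| 90% | 36% v 36% | 5% |
| 80% | 36% v 32% | 8% |
| 70% | 36% v 28% | 20% |

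The capture gaps of 10 and 20 points lie inside the range above, where the gap runs from 0.012/0.40 = 3 to 0.112/0.40 = 28 points. If only the shared interview is used, planned capture is equal and this source of bias disappears.

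**The case against.** The strongest reply is that the stated aim is perceived side effects, which is a patient-reported quantity, and that section 4.1 schedules a monthly interview in both arms to assess exactly that. If the investigators mean to use the interview, capture is symmetric as planned. This stands in part: Aim 1d does not say that sources are pooled, so the bias is conditional on chart data entering. But the rates referred to include adverse events, which section 4.1 draws from medical records, and no sentence confines the comparison to interviews.

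Four stronger readings are tempting and are not supported.
- A reader might infer that Usual Care has nothing but interviews and outside records. Section 8.3 also has adverse-event inquiry at every study visit, and section 4.1 opens the Weill Cornell physicians to both arms, so some Usual Care charts may be abstracted directly.
- A reader might count the Group A monitoring contacts "at weeks 2, 4 and 12 of treatment, and 4 and 12 weeks after the end of treatment" as five extra occasions for eliciting symptoms. Item 8 describes them as blood tests, allows commercial laboratories in some circumstances, and places two of them after treatment. They are not counted above.
- A reader might infer that the DSMB sees the same distortion in ordinary side effects. Section 8.1 says those are not reported to the DSMB, which leaves only the listed safety endpoints.
- A reader might take a net bias against Accessible Care as settled. The set is treated-only, hence selected after randomization, and the study is unblinded (section 9.5). Other biases may act in either direction.

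It is also fair that the stakes are limited: the comparison is conditional on numbers and is not the primary endpoint.

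**Conclusion.** The concern holds in a conditional form. Capture of clinic-recorded events differs by arm by design, and Aim 1d does not keep those events out of the arm comparison. If they enter, the comparison would tend to overstate Accessible Care rates relative to Usual Care at equal true risk.

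The size cannot be derived from the documents. The range of about 1 to 11 points rests wholly on the assumed 40% true rate and the assumed capture rates. The direction refers to this mechanism alone and not to the net bias of the comparison. The sustained virologic response analysis and the sample size are unaffected. The point deserves correction because the remedy is cheap and uses instruments that both arms already have.

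**What to change.** In Aim 1d:
- State that the between-arm comparison of side effects and non-fatal clinical adverse events uses only events elicited by the instruments common to both arms: the monthly on-therapy interview and the adverse-event inquiry at the quarterly research visits. Naming the quarterly visits matters because section 8.3 does not say whether on-site treatment visits count as study visits.
- Count deaths from all sources in both arms, since an interview cannot elicit them.
- Tabulate chart-only events descriptively by arm and source, with the proportion of treated participants in each arm whose treatment records were obtained.
- For the endpoints that section 8.1 lists for safety review (treatment-related SAEs, overdose-related hospitalizations and deaths, overall deaths), keep all events and show their source by arm.

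The cost is a few sentences in the plan and one source variable on the adverse-event form. The downside is that some genuine chart-only events, and non-fatal events in participants who miss interviews, leave the arm comparison. They remain in the descriptive tables and in all safety reporting.

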4.2.2 Secondary Study Endpoints

Aim 2: Substance use. We will report rates of addiction treatment entry and retention;

changes in levels of self-reported alcohol and illicit drug consumption; and urine toxicology results. Outcomes will be examined at 3, 6, and 9 months after randomization, to assess the magnitude and durability of intervention effects. Effect sizes and 95% CIs will be reported.

Aim 3: HIV and HCV risk behaviors. We will report changes in frequency of three injection related and three sexual HIV risk behaviors: (a) injection drug use, (b) use of a syringe previously used by another person, and (c) use of any injection equipment (cooker, cotton, mixing water, mixing syringe, rinse water) previously or simultaneously used by another person, (d) condomless vaginal or anal sex, (e) sex with multiple partners (≥ 2 in past 6 months), and (f) sex in exchange for money or drugs. Outcomes will be reported at 3, 6, and 9 months after randomization, to assess the possibility of transient intervention effects.

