4.2.3 Exploratory Endpoints

Although not a study aim, we will also report quality of life as an additional outcome. Quality of life will be measured using the HQLQ139 at baseline and 3, 6, and 9 months. Scores at 3, 6, and 9 months will be regressed on baseline scores to examine the effect of the intervention as compared with Usual Care. Effect sizes and 95% CIs will be reported for the effect of each intervention.

5 Study Enrollment and Withdrawal

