7.1 Study Procedures/Evaluations

Initial Research Visit (all participants):

1. After signing the consent form, participants will be asked to provide contact information, including your personal telephone number. Also, we will ask participants whether there are friends or family members that we can contact if we have lost contact with you for any reason. No personal health information will be shared with these family or friends. These persons will simply be asked to convey the message that the study team is interested in seeing you. Every month participants will be asked to briefly check in with the study staff, and participants be asked if there are any changes in your contact information.
2. A member of the study team will administer a detailed questionnaire at the time of enrollment into the study. This questionnaire will ask questions about participants' demographics (e.g., age, gender, race), alcohol and drug use history and practices, sexual behavior, and experience with health care.
3. Human Immunodeficiency Virus (HIV) Testing. Participants will have a 10-to 15-minute HIV prevention counseling session with a trained staff member. The session will cover the meaning of results from the HIV test. Participants will also learn about how to reduce your chances of being infected with HIV and other infectious diseases. Participants will get counseling about what the test result means. Participants can get the result of your HIV test within about 20 minutes. Participants will get also get post-test counseling from a trained staff member and referrals to services you may need. If participants already know they have infection with the HIV virus, they may provide results of their HIV test from their medical records instead of doing this test.

At the initial research visit, participants will be randomly assigned to one of these two groups:

Group A: Accessible Care

OR

Group B: Usual Care

If you take part in this study and are assigned to Group A, you will have the following tests and procedures:

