9.1 Statistical and Analytical Plans (SAP)

We will examine a series of study outcomes in both study arms in order to evaluate the effectiveness of the Accessible Care (AC) intervention as compared with Usual Care (UC). Our three Aims are to compare hepatitis treatment, substance use, and HIV and HCV prevention outcomes in the two arms in order to answer three fundamental questions about the AC intervention: (1) Is it sufficiently safe and effective to allow active PWID in appreciable numbers to be successfully treated for hepatitis C? (2) Does it reduce substance use? (3) Does it reduce HIV and HCV risk behaviors? We will assess a multiplicity of outcome measures in order to fully describe the experience of participants in each arm.

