9.5 Measures to Minimize Bias

As described above, participants will be randomized after conducting baseline survey to either the Accessible Care or Usual Care arms. If a participant withdrawals from the study, no replacement will be made.

The study is not blinded.

10 Source Documents and Access to Source Data/Documents

Source data is all information, original records of clinical findings, observations, or other activities in a clinical trial necessary for the reconstruction and evaluation of the trial. Source data are contained in source documents. Examples of these original documents, and data records include: hospital records, clinical and office charts, laboratory notes, memoranda, subjects' diaries or evaluation checklists, pharmacy dispensing records, recorded data from automated instruments, copies or transcriptions certified after verification as being accurate and complete, microfiches, photographic negatives, microfilm or magnetic media, x-rays, subject files, and records kept at the pharmacy, at the laboratories, and at medico-technical departments involved in the clinical trial. It is acceptable to use CRFs as source documents. If this is the case, it should be stated in this section what data will be collected on CRFs and what data will be collected from other sources.

The study case report form (CRF) is the primary data collection instrument for the study. All data requested on the CRF must be recorded. All missing data must be explained. If a space on the CRF is left blank because the procedure was not done or the question was not asked, write "N/D". If the item is not applicable to the individual case, write "N/A". All entries should be printed legibly in black ink. If any entry error has been made, to correct such an error, draw a single straight line through the incorrect entry and enter the correct data above it. All such changes must be initialed and dated. DO NOT ERASE OR

WHITE OUT ERRORS. For clarification of illegible or uncertain entries, print the clarification above the item, then initial and date it.

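### Aim 3 item (e) looks back 6 months but is reported at month 3, when half of that window predates randomisation; any early effect is attenuated at that visit

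*Combined protocol and SAP*

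**What the plan says.** Section 4.2.2 (Aim 3) lists six risk behaviours, three injection-related and three sexual: "We will report changes in frequency of three injection related and three sexual HIV risk behaviors". Item (e) is "sex with multiple partners (≥ 2 in past 6 months", and section 9.2 (Specific Aim 3) repeats the definition. It is the only one of the six with a stated recall period. The reporting times and their purpose are: "Outcomes will be reported at 3, 6, and 9 months after randomization, to assess the possibility of transient intervention effects".

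On timing, section 4.1 states: "Participants in both arms will be interviewed at baseline and 3, 6, and 9 months after randomization". Section 7.1 says: "At the initial research visit, participants will be randomly assigned to one of these two groups". Section 9.5 says that "participants will be randomized after conducting baseline survey to either the Accessible Care or Usual Care arms". The baseline answer therefore lies wholly before assignment.

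Section 9.1 makes the intent comparative: "Our three Aims are to compare hepatitis treatment, substance use, and HIV and HCV prevention outcomes in the two arms". For Aim 3 the plan states no hypothesis test, no power figure and no baseline adjustment. For quality of life, section 4.2.3 does plan an adjusted analysis, in which follow-up scores "will be regressed on baseline scores to examine the effect of the intervention". Nothing in the documents shortens the look-back for item (e) at month 3 or leaves the item out of the month-3 report.

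**The concern.** Behaviour before randomisation cannot differ between arms except by chance. A participant with two or more partners in the 3 months before assignment counts as positive at month 3 whatever happens afterwards. Those same 3 months are also the later half of the baseline window, so baseline and month 3 share half of their recall time. If the intervention has an effect before month 3, both the arm difference and the change from baseline are understated at that visit.

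At stake is how the time course is read, which is the declared purpose of the 3-, 6- and 9-month series. For item (e), the share of the window that follows randomisation rises from 50% at month 3 to 100% at month 6. An immediate lasting effect would then look as if it had built up between the two visits, and a small month-3 difference could be taken as no early effect.

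**Working it through.** **Windows (from the documents).** A 6-month look-back at visit month v covers v-6 to v. The share before randomisation is max(0, 6-v)/6.

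| Visit | Window (months) | Share before randomisation |
|---|---|---|
| Baseline | -6 to 0 | 100% |
| Month 3 | -3 to +3 | 3/6 = 50% |
| Month 6 | 0 to 6 | 0% |
| Month 9 | 3 to 9 | 0% |

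**Size of the attenuation (assumptions).** The plan has no figure for item (e) to reproduce: it gives no partner rate and no expected effect. Assume r = 0.1, 0.25 or 0.5 partners per month, and a relative reduction d = 0.5 or 0.2 in the Accessible Care arm that starts at randomisation and stays constant. The mean counts over 6 months are:

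- control: 6r
- intervention, month 3: 3r + 3r(1-d)
- intervention, month 6: 6r(1-d)

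With Poisson counts of mean m, P(2 or more) = 1 - exp(-m)(1 + m).

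| d | r | Control | Month 3 | Month 6 | Difference, month 3 (points) | Difference, month 6 (points) | Ratio |
|---|---|---|---|---|---|---|---|
| 0.5 | 0.1 | 12.2% | 7.5% | 3.7% | 4.6 | 8.5 | 0.55 |
| 0.5 | 0.25 | 44.2% | 31.0% | 17.3% | 13.2 | 26.9 | 0.49 |
| 0.5 | 0.5 | 80.1% | 65.7% | 44.2% | 14.3 | 35.9 | 0.40 |
| 0.2 | 0.1 | 12.2% | 10.3% | 8.4% | 1.9 | 3.8 | 0.51 |
| 0.2 | 0.25 | 44.2% | 39.1% | 33.7% | 5.1 | 10.5 | 0.49 |
| 0.2 | 0.5 | 80.1% | 75.1% | 69.2% | 5.0 | 10.9 | 0.45 |

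Differences and ratios are from unrounded values.

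**Other count models, same r and d.**

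- Between-person variation: gamma-Poisson with shape k = 0.5, 1 or 2, where p = k/(k+m) and P(2 or more) = 1 - p^k(1 + k(1-p)). The ratio is 0.41 to 0.52.
- Everyone has one steady partner and other partners are Poisson, so the probability is 1 - exp(-m). The ratio is 0.32 to 0.49.

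The overall range is 0.32 to 0.55. A separate set of assumptions (6-month prevalence 20-50%, rate ratio 0.5 or 0.7, Poisson and gamma-Poisson) gave 0.41 to 0.53.

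**Does month 3 still carry information?** Take r = 0.25, d = 0.5 and Poisson counts, and compare two time courses:

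- Effect d confined to months 3-6: means 6r = 1.5 at month 3 and 6r - 3rd = 1.125 at months 6 and 9. Differences at months 3/6/9: 0/13.2/13.2 points.
- Lasting effect of half the size, d/2: means 6r - 1.5rd = 1.3125 at month 3 and 1.125 at months 6 and 9. Differences: 6.5/13.2/13.2 points.

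Months 6 and 9 cannot tell these apart; month 3 can. Conversely, an effect confined to months 0-3 gives 13.2/13.2/0 points, so month 9 is what identifies an early transient effect.

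**The case against.** The strongest objection is to going further and removing the month-3 comparison, on the ground that a diluted estimate is worth nothing. That does not follow. The comparison is randomised and unbiased between arms, and the last calculation shows a case in which it alone separates a transient from a lasting effect. Dropping it would work against the plan's own purpose. This objection stands in full, and the fix keeps month 3.

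A reader might also infer that month 3 is uniquely uninformative, because under a 20% reduction every month-3 difference is smaller than its 95% confidence half-width with 150 per arm. The same is true of 14 of the 15 month-6 differences (for example 10.5 points against 11.0). A 20% effect is hard to see at any visit, so that is no argument against month 3 in particular.

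The 32-55% range needs an immediate effect, and the documents do not promise one for partner number. Section 7.1 (Group A, item 10) allows the harm-reduction meeting at any time in the first 6 months and lists HCV transmission and injection topics. HIV prevention counselling at the initial visit goes to everyone. If an effect starts later, month 6 is diluted too and the range does not apply. This stands as a limit on the size, not on the 50% overlap.

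Finally, the questionnaire is not among the documents and may ask about a shorter period at follow-up. If so, the definition in the plan is what needs correcting. And item (e) is one of six secondary behaviours with no stated test, which is why the point is minor.

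**Conclusion.** The point holds in a limited form. As the plan defines item (e), exactly half of the month-3 window predates randomisation and overlaps the baseline window; this follows from the documents alone. If there is a real effect before month 3, the month-3 arm difference and the change from baseline are attenuated. The arm difference falls to roughly 32-55% of the month-6 value if the effect is immediate and constant, under assumed partner rates of 0.1 to 0.5 per month and reductions of 20% or 50%.

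A reader might infer that the arms are biased against each other or that the trial's conclusion is at risk. Neither is supported: the pre-randomisation months affect both arms alike, there is no dilution when there is no effect, and SVR and the sample size are untouched. Severity is minor.

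**What to change.** Change SAP wording only, in sections 4.2.2 and 9.2:

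1. *Item (e) will be compared between arms mainly at months 6 and 9 (windows 0-6 and 3-9 months after randomisation). The month-3 comparison is supportive. It will be labelled as covering 3 months before to 3 months after randomisation and will not be read as evidence of no early effect or of later growth.*
2. *Comparisons of item (e) will be adjusted for its baseline value.* This follows the approach already planned for quality of life in section 4.2.3. It adds precision but does not remove the dilution, so step 1 is still needed.

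The questionnaire and visits stay as they are, and the baseline value is already collected. The cost is that month 3 carries less weight for this one item. The other five behaviours keep month 3 unchanged, since the plan states no 6-month window for them.
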